3.6.2 Lost to Follow-Up

All reasonable efforts must be made to locate subjects to determine and report their ongoing status. This includes follow-up with persons authorized by the subject as noted above. Lost to follow-up

is defined by the inability to reach the subject after a minimum of three documented phone calls, faxes, or emails as well as lack of response by subject to one registered mail letter. All attempts should be documented in the subject's medical records. If it is determined that the subject has died, the site will use permissible local methods to obtain the date and cause of death.

If investigator's use of third-party representative to assist in the follow-up portion of the study has been included in the subject's informed consent, then the investigator may use a Sponsor-retained third-party representative to assist site staff with obtaining subject's contact information or other public vital status data necessary to complete the follow-up portion of the study. The site staff and representative will consult publicly available sources, such as public health registries and databases, in order to obtain updated contact information. If after all attempts, the subject remains lost to follow-up, then the last known alive date as determined by the investigator should be reported and documented in the subject's medical records.

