Death without prior progression and no new anticancer treatment started	Date of death	Progressed

Table 4.2-1:Censoring Scheme for PFS

OS is defined as the time from the date of first dose of study drug until the date of death (any reason). If the subject is alive or the vital status is unknown, the subject will be censored at the date the subject was last known to be alive.

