8 CONVENTIONS

The following conventions may be used for imputing partial dates for analyses requiring dates:

- For missing and partial adverse event onset dates, imputation will be performed using the Adverse Event Domain Requirements Specification⁹.
- Missing and partial Non-Study Medication Domain dates will be imputed using the derivation algorithm described in 4.3.3 of BMS Non-Study Medication Domain Requirements Specification¹⁰.

For death dates, the following conventions will be used for imputing partial dates:

- If only the day of the month is missing, the 1st of the month will be used to replace the missing day. The imputed date will be compared to the last known date alive and the maximum will be considered as the death date.
- If the month or the year is missing, the death date will be imputed as the last known date alive. If the date is completely missing but the reason for death is present the death date will be imputed as the last known date alive

For date of progression, the following conventions will be used for imputing partial dates:

- If only the day of the month is missing, the 1st of the month will be used to replace the missing day*.
- If the day and month are missing or a date is completely missing, it will be considered as missing.
- In case of the date of death is present and complete, the imputed progression date will be compared to the date of death. The minimum of the imputed progression date and date of death will be considered as the date of progression.
- For other partial/missing dates, the following conventions may be used:
- If only the day of the month is missing, the 15th of the month will be used to replace the missing day.
- If both the day and the month are missing, "July 1" will be used to replace the missing information.
- If a date is completely missing, it will be considered as missing.

The following conversion factors will be used to convert days to months or years:

1 month = 30.4375 days and 1 year = 365.25 days.

Duration (e.g. time from first diagnosis of NSCLC to first dosing date, duration response, and time to response) will be calculated as follows:

Duration = (Last date - first date + 1)

All statistical analyses will be carried out using SAS (Statistical Analysis System software, SAS Institute, North Carolina, USA) unless otherwise noted.

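### SAP 8 discards the recorded year when a death's month is missing, so a death can be dated in a year the record rules out and OS for that subject is too short

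*SAP*

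**What the plan says.** SAP 8 (Conventions) opens by saying that its conventions may be used, but the death-date rules carry a firmer instruction: "For death dates, the following conventions will be used for imputing partial dates". Three cases follow.

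- Only the day missing: the first of the recorded month is substituted, and then "The imputed date will be compared to the last known date alive and the maximum will be considered as the death date".
- Month or year missing: "If the month or the year is missing, the death date will be imputed as the last known date alive".
- Date wholly missing: "If the date is completely missing but the reason for death is present the death date will be imputed as the last known date alive".

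SAP 8 does keep a known year for dates other than death and progression: when day and month are missing, it substitutes July 1.

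The death date feeds several analyses. OS runs from first dose to death (SAP 4.2). In SAP Table 4.2-1, the row "Death without prior progression and no new anticancer treatment started" counts as a PFS event on the date of death. DOR and duration of CR also end at death. SAP 7.5.2 plans Kaplan-Meier medians and says that 6- and 12-month PFS and OS rates may be reported. Nothing elsewhere in the protocol or SAP overrides the death-date rule.

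**The concern.** The second rule puts two different situations together. If the year is missing, nothing usable is known beyond the last contact. If the year is present and only the month (with or without the day) is missing, the record still shows that the subject was alive until at least 1 January of that year. The rule discards that fact. Whenever the last known alive date lies in the preceding year or before, the analysis date of death contradicts the recorded year.

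At stake is OS, which protocol 3.6 calls a key endpoint. An affected subject leaves the risk set as a death at a time when the record shows the subject alive. In subtype groups planned at 10 to 40 subjects, one such subject could be visible in a landmark rate.

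**Working it through.** The plan gives no figure on this point, so there is none to reproduce. The rule can be applied literally to example subjects.

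**Inputs from the documents.** Death-date rules, duration = last date − first date + 1, and 1 month = 30.4375 days (all SAP 8). Survival contact at least every 3 months (protocol 3.1). Planned Cohort B sizes: 40 DLBCL, 30 PTCL, 20 CTCL, 30 PMBL, 10 MGZL (SAP 5.1).

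**Assumptions for illustration.** First dose 10 January 2017; death recorded as 2018 with month and day missing; various last known alive dates.

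**Formulas.** SAP date = last known alive date. Earliest date compatible with the record = later of 1 January 2018 and the last known alive date. Gap = the second minus the first.

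| Last known alive | OS under SAP 8 (months) | OS to earliest compatible date (months) | Gap (days) |
|---|---|---|---|
| 20 Dec 2017 | 11.33 | 11.73 | 12 |
| 15 Nov 2017 | 10.18 | 11.73 | 47 |
| 2 Oct 2017 | 8.74 | 11.73 | 91 |
| 1 Jul 2017 | 5.68 | 11.73 | 184 |
| 10 Feb 2018 | 13.04 | 13.04 | 0 |

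The 2 October row in full: 10 January to 2 October 2017 is 265 days, so OS = (265 + 1)/30.4375 = 8.74 months. To 1 January 2018 it is 356 days, so (356 + 1)/30.4375 = 11.73 months. The gap is 356 − 265 = 91 days, or 2.99 months.

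**Reading the table.** The first three rows fit a 3-monthly contact schedule. The 184-day row requires contact to have lapsed. The last row shows that no impossible date arises when the last alive date is already in the death year.

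**Landmark rates.** A rate at 6 or 12 months changes materially only if the landmark lies between the SAP date and the corrected date. In the table, no row crosses 12 months and only the 1 July row crosses 6 months. Crossing depends on the first-dose date as well as the gap. With first dose on 1 May 2017 and last alive 2 October 2017, OS moves from (154 + 1)/30.4375 = 5.09 to (245 + 1)/30.4375 = 8.08 months, which crosses 6 months with contact still on schedule.

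**Size of one crossing.** Without censoring, one subject moves the rate by 1/n: 1/10 = 10 points in MGZL, 1/20 = 5 in CTCL, 1/30 = 3.3 in PTCL or PMBL, and 1/40 = 2.5 in DLBCL. SAP 7.1 pools Cohort A with Cohort B by subtype, so n is larger, and the shift smaller, wherever Cohort A contributes subjects.

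**The case against.** The best defence is that this matters little. It needs a death with the year known, the month unknown and the last contact in an earlier year. The documents give no expected number of such deaths, and 3-monthly contact, with extra survival checks at the sponsor's request (protocol 3.6), should keep them few. ORR does not use death dates. OS and PFS are secondary and descriptive, and for OS the error is in the conservative direction for a single-arm trial. All of that stands, and it limits the importance of the point. It does not justify an event date that the record excludes.

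Several stronger readings are tempting, but the documents do not support them.

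- *Survival rates and medians are biased downward in general.* A landmark rate moves materially only when the correction crosses it, and one subject may not move a median at all.
- *The error typically runs to many months.* That requires contact to have lapsed well beyond the 3-month interval.
- *Year-only deaths will cluster in subjects lost to follow-up.* Protocol 3.6.2 says only: "If it is determined that the subject has died, the site will use permissible local methods to obtain the date and cause of death". It is silent on incomplete dates, so this is plausible inference and no more.
- *The rule also discards known progression-free time.* A recorded death year shows that the subject was alive, not that the subject was progression-free.
- *SAP 8 contradicts itself.* The day-missing and month-missing rules cover different cases, and both impute early. The second is coarser, but the two do not conflict.

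**Conclusion.** The point holds for OS and is minor. Followed as written, SAP 8 can place a death in a calendar year that the record rules out, which the day-missing rule cannot do. OS for such a subject is too short by up to about 3 months if survival contact is kept, and by more only if it lapsed. The effect on a 6- or 12-month OS rate is nil or close to it unless the correction crosses the landmark; if it does, the shift is at most about 1/n per subject without censoring. The example dates are assumptions, and the number of affected deaths cannot be estimated from the documents.

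For PFS, DOR and duration of CR the case is weaker. The imputed death date is just as impossible, but a later date would count time in which progression status was not observed. PFS is not affected where new anticancer therapy came before the death, because Table 4.2-1 then censors it.

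**What to change.** Split the month-or-year rule in SAP 8:

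- Year known, month missing: set the death date to the later of 1 January of the recorded year and the last known alive date.
- Year missing, or the whole date missing: keep the last known alive date, as now.

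This extends the logic of the day-missing rule and changes nothing when the last alive date already falls in the death year. It costs one SAP sentence and one line of code, with no new data. There is a small downside: where the death also ends PFS, DOR or duration of CR, those durations may lengthen slightly through unobserved time. The SAP should acknowledge this when the rule is changed.

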9 CONTENT OF REPORTS

All analyses describe in this SAP will be included in the final Clinical Study Report. Refer to the Data Presentation Plan for mock-ups of all tables and listings. Analyses of the different NHL subtype may not be conducted all at the same time depending on accrual in the different group.

10 DOCUMENT HISTORY

Table 10-1:	Document History		
Version Number	Author(s)	Description	
1.0		Initial version: January 31, 2017
